1.0 Objectives / Specific Aims

The goal of this work is to develop, refine, and pilot test an electronic visit (e-visit) to: 1) deliver smoking cessation treatment to adults at risk for COPD and 2) to improve rates of COPD early detection and accurate diagnosis. We will conduct a pilot RCT (N=100, up to 120 assuming 20% attrition) of the COPD/smoking cessation e-visit as compared to treatment as usual (TAU), with primary objective to provide effect size estimates for a larger RCT. Specific aims are twofold:

Aim 1: Conduct usability testing of the smoking cessation/COPD e-visit with patients (N=5, up to 10 to account for attrition) followed by iterative refinements consistent with participant feedback.

Aim 2: Conduct a pilot, small-scale randomized controlled trial to examine COPD and smoking cessation outcomes associated with the E-Visit as compared to treatment as usual (TAU; i.e., no e-visit). Outcomes will include those related to: e-visit feasibility (i.e., time to complete e-visit, time for provider to review e-visit, % completed e-visits, qualitative feedback), COPD (early diagnosis rates as a function of treatment condition, emergency department visits for respiratory infection), smoking cessation outcomes (self-reported quit attempts/quit duration and biochemically verified cessation via carbon monoxide), and cessation medication utilization.

We hypothesize that participants randomized to the e-visit condition as compared to those randomized to the TAU condition will have higher (numerically, if not statistically significant) rates of COPD early diagnosis, cessation treatment utilization (medications, counseling), and superior cessation-related outcomes.

2.0 Background

More than 16 million Americans have COPD and millions more suffer from COPD but have not yet been accurately diagnosed or treated¹. Nationwide healthcare costs associated with COPD exceed \$36 billion annually and are projected to reach \$49 billion by 2020¹. COPD is now concentrated within rural communities and those who reside in rural areas as compared to those who reside in large metropolitan areas have both higher COPD incidence (8% vs. 5%) and higher COPD-related death rates (55 per 100,000 vs. 32 per 100,000)². Telehealth strategies to implement evidence-based best practice for COPD may be particularly impactful among rural communities as such treatment modalities can extend the reach of traditional COPD prevention, diagnosis, and treatment strategies.

In light of the significant public health impact of COPD, the National Heart Lung and Blood Institute (NHLBI) issued a COPD National Action Plan in 2017. A key goal within this national action plan is to improve the diagnosis, prevention, treatment, and management of COPD by improving the quality of care delivered across the health care continuum. Informed by this federal national action plan, and with the guidance of HRSA, our team will undertake a 22-month planning and pilot intervention period to identify how telehealth modalities might be optimally leveraged to improve the quality of care and outcomes among patients at risk for COPD. Because COPD is most commonly caused by cigarette smoking, we will focus our planning and intervention period specifically on COPD early detection among cigarette smokers and on leveraging telehealth to extend the reach of evidence-based smoking cessation treatment (i.e., medications and counseling for smoking cessation) for those at risk for COPD. This work will build upon and extend our team's ongoing efforts to develop a smoking cessation electronic visit (e-visit) that can be proactively delivered to all adult MUSC patients who have been identified via the electronic health record as cigarette smokers. E-visits are embedded into the most common electronic health record (EHR) systems (e.g., Epic, Allscripts, and others) and offer a secure platform through which patients can

remotely supply providers with health information. Providers in turn can deliver personalized instructions and/or treatment to the patient. Prior studies of asynchronous e-visits for chronic condition treatment have found high satisfaction among both patients and providers and that such e-visits can be delivered efficiently (average time for patient to complete e-visit = 8.3 minutes, average time for provider to review and respond to e-visit = 3.6 minutes)³.

Our team received a pilot award (PIs: [name] and [name]) from the South Carolina Telehealth Alliance in July 2018 to begin development of a smoking cessation e-visit for implementation within MUSC primary care. Preliminary e-visit development is now complete and a pilot trial to examine smoking cessation outcomes associated with e-visit receipt is underway. Herein, we will leverage this proactive, scalable platform to: 1) deliver smoking cessation treatment to adults at risk for COPD and 2) to improve rates of COPD early detection and accurate diagnosis. The ultimate goal of this line of work is to improve the quality of care and associated outcomes among patients at risk for COPD.

3.0 Intervention to be studied

We are currently in the process of modifying our existing asynchronous smoking cessation e-visit to incorporate COPD early detection with MUSC's BMIC Epic development team. The smoking cessation component of the e-visit is based on USPHS guidelines⁴ and serves to automate much of the 5As (i.e., Ask, Advise, Assess, Assist, Arrange) process. Smokers are proactively invited via electronic message (e.g., via MyChart) to initiate an asynchronous smoking cessation e-visit. The e-visit is a questionnaire administered via MyChart. The initial asynchronous e-visit gathers information about smoking and quit histories, followed by questions to assess motivation to quit and an algorithm to determine the best smoking cessation medication to prescribe for each patient by assessing contraindications and preferences for FDA-approved first line cessation medications (i.e., nicotine replacement therapy, varenicline, bupropion). The e-visit will be sent to an attending physician (study physicians included on the IRB protocol), who will review the recommendations, inform study staff of which medication to provide to participants, make referrals to additional smoking cessation resources (e.g., state quitline), and schedule a follow-up e-visit. Varenicline, a class C medication, may be provided as a result of the e-visit. Because risks during pregnancy related to Varenicline are unknown, women under the age of 55 who receive a recommendation for Varenicline as a result of the e-visit algorithm will subsequently be asked if they would be willing to complete a pregnancy test that will be mailed to them. Women under the age of 55 who respond "No" to this item will not be prescribed Varenicline. The follow-up e-visit will assess tobacco use, medication adherence, side effects, and determine if further cessation treatment is needed (e.g., an additional follow-up e-visit, referral to counseling). All patients will be scheduled for at least one follow-up e-visit within a month after the initial e-visit. E-visits will also include a SmartSet (i.e., a group of orders and other elements that are commonly used together to document a specific type of visit) to streamline provider documentation and treatment plans. E-visits typically delivered for clinical purposes via Epic at MUSC cost \$25, but this cost will be waived for participants in this study.

For the purpose of this trial, this initial asynchronous e-visit will also include an assessment of COPD symptoms via the COPD Assessment in Primary Care to Identify Undiagnosed Respiratory Disease and Exacerbation Risk (CAPTURE)⁵. Those who score ≥ 2 on the CAPTURE will be considered symptomatic and will be invited to complete additional COPD screening measures. These individuals will be mailed a home spirometer and will be asked to complete an additional e-visit during which they will upload a video of themselves completing home spirometry via the device. The home spirometer will measure peak expiratory flow (PEF), forced expiratory volume (FEV1 and FEV6), and forced vital capacity (FVC). These videos will be reviewed by a study attending physician and follow-up care will be provided consistent with best clinical practices. In addition to home spirometry, all patients who screen positive on

the CAPTURE during the baseline e-visit will be referred to an in person appointment for spirometry/bronchodilation consistent with best practices.

Participants enrolled in the present study who are randomized to the TAU condition will be provided information about the state quitline and about the importance of quitting smoking and it will be recommended that they contact their PCP to schedule a medical visit to discuss quitting smoking.

4.0 Study Endpoints (if applicable)

Primary outcome variables include:

- Evidence-based cessation treatment utilization will be assessed via participant self-report. At each follow-up assessment, participants in both groups will be queried for: 1) use of a smoking cessation medication since the last assessment, 2) how the medication was obtained (e.g., via the study or another outlet such as MUSC's existing smoking cessation service), and 3) receipt of the 5As from their PCP⁶.
- Cessation-related outcomes will be assessed via participant self-report. Cigarette smoking, use of other tobacco products (e.g., e-cigarettes), and quit attempts/quit duration will be assessed at each follow-up using a timeline followback for the last 6-months at baseline and since prior follow-up for each subsequent assessment^{7,8}.
- COPD diagnosis will be assessed both via established metrics captured via home spirometry and via chart review.

Secondary outcome variables include:

- E-visit acceptability and feasibility will be assessed both by examining the percentage of patients who complete the initial and follow-up e-visits, and by participant self-report during follow-up assessments. Participants will respond to items assessing ease of use, satisfaction, and pros/cons of the e-visit. Analytics data (e.g., amount of time it takes to complete the e-visit, amount of time it takes the provider to review the e-visit) will also be collected as will data on provider fidelity to e-visit recommendations (captured by reviewing within Epic whether the provider administered treatment consistent with e-visit recommendations).

We will also assess:

- Nicotine dependence will be assessed at baseline via the Fagerstrom Test of Nicotine Dependence⁹.
- Motivation to quit and confidence in quitting will be assessed via participant self-report using a modified Contemplation Ladder¹⁰.

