that only FDA approved cessation medications will be recommended, which include nicotine replacement therapy (patch, gum, lozenge), varenicline, or bupropion. Medications will only be recommended if a participant does not have a contraindication for that medication. Women who indicate during the e-visit that they are currently pregnant or are planning to become pregnant within the next 6 months will not receive a medication recommendation/prescription as a result of the e-visit. These women will receive a counseling referral. Any woman under the age of 55 who receives a varenicline recommendation as a result of the e-visit will subsequently be asked within the e-visit if she is willing to complete a pregnancy test that will be mailed to her at no cost to verify that she is not pregnant prior to taking varenicline.

Women under the age of 55 who respond “Yes” to this item will be mailed a pregnancy test by study staff and will be required to verify (with signature) that they completed the test and are not pregnant via REDCap. Women under the age of 55 who respond “No” to this item will not receive varenicline as a result of the e-visit. These women instead will either receive NRT, bupropion and/or counseling based on other contraindications and medication preferences indicated throughout the e-visit. Participants will be scheduled for a follow-up e-visit one month following their initial e-visits. The follow-up e-visit may also result in a medication recommendation that will be e-prescribed and mailed to the participant as outlined above for the baseline e-visit. If randomized to the TAU condition, participants will be provided information on quitting smoking, including information about the state quitline, and will be provided a recommendation to contact their PCP to schedule a medical visit to discuss quitting smoking.

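### The hypothesis counts counselling as treatment utilisation, but no listed follow-up item measures counselling or quitline use

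*Combined protocol and SAP*

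**What the plan says.** **The construct.** The hypothesis in Section 1.0 is that the e-visit arm will have higher "rates of COPD early diagnosis, cessation treatment utilization (medications, counseling), and superior cessation-related outcomes". Section 2.0 uses the same scope: "evidence-based smoking cessation treatment (i.e., medications and counseling for smoking cessation"). Aim 2, also in Section 1.0, is narrower and ends its outcome list with "and cessation medication utilization".

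**The measurement.** Section 4.0 makes evidence-based treatment utilisation a primary outcome, assessed by self-report. At each follow-up, both groups are "queried for: 1) use of a smoking cessation medication since the last assessment, 2) how the medication was obtained"; the third and last item is "receipt of the 5As from their PCP". Section 10.0 repeats this list.

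**What the arms are offered.** Under Section 3.0 the physician reviewing an e-visit makes referrals to further resources, with the state quitline as the example, and the follow-up e-visit may lead to a counselling referral. For women who report being pregnant or planning pregnancy, Section 10.0 gives no medication recommendation and says: "These women will receive a counseling referral". TAU participants "will be provided information about the state quitline and about the importance of quitting smoking" and are advised to see their PCP (Sections 3.0 and 10.0).

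**The analysis.** Section 11.0 names utilisation as a primary smoking-related outcome, with medication given as an example. It plans Fisher's exact test with 67 and 33 participants and assumes rates of 48% and 11%, for 95% power. It does not say how the three items become a yes/no outcome.

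**The concern.** Counselling is half of the construct named in the hypothesis, and the quitline is a resource to which both arms are directed, yet the listed items give neither a data source. A participant in either arm who calls the quitline and takes no medication leaves no trace in them. The 5As item does not fill the gap: it concerns what the PCP did, and at most touches on referral, not on whether counselling was taken up.

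This matters because the pilot's stated primary objective is to supply effect sizes for a larger trial. If that trial defines utilisation as the hypothesis does, the pilot will have no estimate for the counselling component or for medication and counselling combined. Uptake is self-reported over the interval since the last assessment, so the time to ask is at the 1- and 3-month questionnaires.

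**Working it through.** **1. Match each part of the construct to an item.**

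| Component | Named in the plan | Listed follow-up item |
|---|---|---|
| Cessation medication | Sections 1.0, 2.0, 11.0 | Yes: use and source, both arms |
| Counselling, including quitline | Sections 1.0 and 2.0; referral or information in 3.0 and 10.0 | None |
| 5As | Section 4.0 | PCP only |

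**2. Reproduce the plan's power.** Inputs from Section 11.0: p1 = 0.48, p2 = 0.11, n1 = 67, n2 = 33. Alpha and sidedness are not stated; I assume two-sided 0.05.

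- Pooled rate: (67 × 0.48 + 33 × 0.11)/100 = 0.358.
- Null standard error: √[0.358 × 0.642 × (1/67 + 1/33)] = 0.102.
- Alternative standard error: √(0.48 × 0.52/67 + 0.11 × 0.89/33) = 0.0818.
- Normal approximation: Φ[(0.37 − 1.96 × 0.102)/0.0818] = 98.1%.
- With continuity correction, subtracting ½(1/67 + 1/33) = 0.0226 from 0.37: 96.4%.
- Exact enumeration of Fisher's two-sided test: 97.7%.

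The stated 95% is close to the continuity-corrected value and, if anything, conservative. For quit attempts (24% vs 6%), exact Fisher power is 60.1% against the stated 60%.

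**3. See how counting counselling could move the difference.** The documents give no counselling or quitline rates, so the uptake figures are assumptions. I read 48% and 11% as medication rates. Let a and t be the proportions of non-medication users who use counselling in the e-visit and TAU arms.

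- Combined e-visit rate = 0.48 + 0.52a
- Combined TAU rate = 0.11 + 0.89t
- Difference = 0.37 + 0.52a − 0.89t

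| a | t | E-visit | TAU | Difference (points) | Fisher power |
|---|---|---|---|---|---|
| 0 | 0 | 48.0% | 11.0% | 37.0 | 97.7% |
| 10% | 10% | 53.2% | 19.9% | 33.3 | 89.0% |
| 20% | 20% | 58.4% | 28.8% | 29.6 | 76.3% |
| 0 | 20% | 48.0% | 28.8% | 19.2 | 39.8% |
| 20% | 0 | 58.4% | 11.0% | 47.4 | 99.9% |

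The difference is linear in a and t, so over the range 0 to 20% its limits are 19.2 and 47.4 points. With equal uptake u it becomes 0.37(1 − u) and shrinks. It is unchanged when 0.52a = 0.89t, that is, when a is 1.71 times t, and grows when a is larger than that. Nothing in the documents says which case applies.

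**The case against.** The best defence is that the primary outcome is really medication use. Aim 2 lists only medication utilisation, and Section 11.0 offers medication as its example. Medication is asked about identically in both arms and credited whatever its source, so leaving out counselling narrows the construct without biasing that contrast. This stands. It does not remove the gap, because the hypothesis still names counselling and Section 11.0 gives an example, not a definition.

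A second point is that Sections 4.0 and 10.0 summarise the questionnaire, which is not itself in the documents. That is why the claim is limited to listed items. E-visit completion and provider fidelity are recorded, but as feasibility measures for the e-visit arm, and they do not show whether anyone used counselling.

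A reader might infer that the omission exaggerates the e-visit's effect because TAU is mainly pointed to the quitline. For example, adding 2 points to the e-visit arm and 15 to TAU gives 50% vs 26%, a 24-point difference with 58.8% Fisher power. That scenario assumes its own direction. The e-visit arm is referred to the quitline too, and active referral could produce more uptake there.

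A reader might also see the PCP-only 5As item as unfair to the e-visit, which automates much of the 5As. Crediting the e-visit would largely re-measure receipt of the intervention. An item limited to the PCP is a defensible description of usual care, which Section 14.0 says the study will not augment.

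Finally, the group sent only to counselling is probably small: pregnancy or planned pregnancy in a trial of people aged 40 or over.

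**Conclusion.** The mismatch is real. The hypothesis covers medications and counselling, and the listed items leave counselling and quitline uptake unmeasured in both arms. As written, the trial cannot estimate that part of its hypothesised primary effect.

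The documents do not support the stronger inference that the primary effect size is distorted. That would require an analysed outcome broader than medication use, and no section defines one. The direction and size of any change are unknown: the 19-to-47-point range, with Fisher power from about 40% to over 99%, rests on assumed uptake of 0 to 20% among non-medication users, on reading 48% and 11% as medication rates, and on a two-sided 0.05 test. It shows how sensitive a combined outcome would be and does not forecast a result. Neither the 95% nor the 60% power figure needs correction.

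**What to change.** Add one item to the 1- and 3-month questionnaires in both arms: any cessation counselling since the last assessment (quitline, individual or group), and its source.

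In Sections 4.0 and 11.0:

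- define the binary outcome for Fisher's exact test as any cessation medication use, to which the 48% vs 11% planning rates would apply;
- report counselling or quitline use, and medication-or-counselling use, by arm as separate estimates;
- keep PCP 5As as a descriptive component outside the binary outcome.

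There is no need to make the combination the primary endpoint, since the documents give no planning rates for it, or to reword the 5As item to include the e-visit.

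The cost is one short question and a definition. The combined difference may turn out smaller or larger than 37 points, and the report should be prepared for either.

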5.0 Inclusion and Exclusion Criteria/ Study Population

Participants will complete a survey within MyChart to be screened for eligibility. Inclusion criteria for patients across aims include: 1) current smoking, defined as smoking 5+ cigarettes/day, for 20+ days out of the last 30, for the last 6+ months, 2) age 40+, 3) enrolled in Epic's MyChart program or willing to sign up for MyChart, 4) possess a valid e-mail address that is checked daily to access follow-up assessments and MyChart messages, 5) English fluency, and 6) owner of an iOS or Android-compatible smartphone and a webcam-enabled device (necessary for providing carbon monoxide readings). As an aim of this study is to facilitate COPD early diagnosis, participants will be excluded if they have COPD on their problem list within Epic. Inclusion criteria for providers for usability testing include: 1) medical provider at MUSC and 2) treat adult patients.

6.0 Number of Subjects

We will recruit up to 10 patients for usability testing and 120 subjects for the pilot RCT.

7.0 Setting

Research will be conducted remotely via REDCap and MyChart. Participants will be recruited remotely and will be MUSC patients.

8.0 Recruitment Methods

Participants will be recruited in the following ways:

- 1) Via MyChart: MUSC patients who have previously been identified as smokers will be sent a secure message via MyChart inviting them to complete a preliminary eligibility screening. **These patients will have either agreed to research contact within MyChart or their attending physician will have agreed to contact their patients who smoke cigarettes via MyChart.** Within the message, potential participants will be invited to click a link to complete an eligibility screening via MyChart.
- 2) In Clinic: Participants may be recruited in clinic either after being identified as a smoker by research personnel listed on this application.
- 3) Via advertisements (e.g., flyers) and online postings

Note, that while we include the options to recruit in clinic and via advertisements, these will be used as backup options should recruitment via MyChart be slow and/or result in an insufficient number of participants recruited.

Recruitment of Minority Smokers

Minority smokers will be included in this trial. All participants will be recruited from MUSC practices, which primarily serve residents of Charleston County, South Carolina. United States Census data from 2015 (the most recent Census year available) reveal that the population within Charleston County is 68.2% White, 28.1% Black, 2.2% American Indian/Alaskan Native, Asian, or Pacific Islander, 1.5% reporting two or more races, and 5.0% are Hispanic or Latino. Compared to Charleston County demographics, members of racial and/or ethnic minority groups tend to be overrepresented among smokers treated via MUSC's clinics. Roughly half of smokers treated via these clinics are members of a racial or ethnic minority group. We will monitor closely our minority recruitment goals on an ongoing basis. If the recruitment of minorities is lower than expected (< 10% projected enrollment), efforts will be made to improve recruitment of minorities into the study through oversampling.

